5.5. Concomitant Medications

Although acetaminophen at doses of \leq 2 grams/day is permitted, it should be used with caution in subjects with impaired liver function.

Medications or vaccinations specifically prohibited in the exclusion criteria are not allowed during the ongoing trial. If there is a clinical indication for one of these or other medications or vaccinations specifically prohibited during the trial, discontinuation from trial therapy or vaccination may be required. The investigator should discuss any questions regarding this with the sponsor-investigator by contacting the HCRN Project Manager. The final decision on any supportive therapy or vaccination rests with the investigator and/or the subject's primary physician.

5.5.1. Permitted Concomitant Medications and Procedures

All treatments that the investigator considers necessary for a subject's welfare may be administered at the discretion of the investigator in keeping with the community standards of medical care including transfusion of blood and blood products, treatment with antibiotics, analgesics, erythropoietin, or bisphosphonates, when appropriate. All concomitant medications will be recorded on the electronic case report form (eCRF).

All concomitant medications received within 28 days before the first dose of trial treatment and 30 days after the last dose of trial treatment should be recorded. Concomitant medications administered beyond 30 days after the last dose of trial treatment should be recorded for SAEs as defined in Section 11.

Myeloid growth factors to treat subjects with neutropenia according to the American Society of Clinical Oncology (ASCO) Guidelines are permitted. Myeloid growth factors should be avoided (if medically appropriate) in Cycle 1 until subjects have developed a dose-limiting Grade 4 neutropenia.

Antiemetic agents may be administered at the discretion of the investigator but are not commonly required as a prophylactic agent. All other manifestations of the subject's malignancy should be treated at the discretion of the investigator.

Medications with potential central nervous system (CNS) effects are not prohibited in this study, but it is recommended that their use be minimized to avoid confusion in the interpretation of CNS effects should they occur during the course of treatment with ramucirumab and nivolumab.

In appropriate settings, such as combinations with agents known to produce frequent thrombocytopenia, restricted uses of anticoagulants should be considered.

All other medical conditions should be treated at the discretion of the investigator in accordance with local community standards of medical care.

5.5.2. Prohibited Concomitant Medications

Subjects are prohibited from receiving the following therapies during the Screening and Treatment Phase of this trial:

- Anti-cancer systemic chemotherapy or biological therapy not specified in this protocol
- Immunotherapy not specified in this protocol
- Concomitant use of chemotherapy
- Investigational agents other than ramucirumab or nivolumab
- Radiation therapy
- Live vaccines within 30 days prior to the first dose of trial treatment and while participating in the trial. Examples of live vaccines include, but are not limited to, the following: measles, mumps, rubella, chicken pox, yellow fever, rabies, BCG, and typhoid (oral) vaccine. Seasonal influenza vaccines for injection are generally killed virus vaccines and are allowed; however, intranasal influenza vaccines (e.g. Flu-Mist®) are live attenuated vaccines, and are not allowed.

- Systemic glucocorticoids for any purpose other than to modulate symptoms from an event of clinical interest of suspected immunologic etiology. The use of physiologic doses of corticosteroids is allowed.

Subjects who, in the assessment by the investigator, require the use of any of the aforementioned treatments for clinical management should be removed from the trial.

There are no prohibited therapies during the Post-Treatment Follow-up Phase.

5.6. Diet/Activity/Other Considerations

5.6.1. Diet

Subjects should maintain a normal diet unless modifications are required to manage an AE such as diarrhea, nausea, or vomiting.

5.6.2. Contraception

Ramucirumab and nivolumab may have adverse effects on the composition of sperm or on a fetus *in utero*. Investigators shall counsel WOCBP, and male participants who are sexually active with WOCBP, on the importance of pregnancy prevention and the implications of an unexpected pregnancy, the potential of fetal toxicity occurring due to transmission of study drug, present in seminal fluid, to a developing fetus, even if the participant has undergone a successful vasectomy or if the partner is pregnant.

Women of childbearing potential (WOCBP) must be willing to use two methods of birth control. The two birth control methods can be either two barrier methods or a barrier method plus a hormonal method to prevent pregnancy. WOCBP should begin using birth control from the screening visit, throughout the study period, and up to 5 months following the last dose of study drugs. Total abstinence for the same study period is an acceptable alternative. Women of non childbearing potential or considered highly unlikely to conceive are defined as 1) surgically sterilized, or 2) postmenopausal (a woman who is ≥ 45 years of age and has not had menses for greater than 1 year will be considered postmenopausal), or 3) not heterosexually active for the duration of the study.

Men who are not surgically or medically sterile must agree to use an acceptable method of contraception. Male subjects with female sexual partners who are pregnant, possibly pregnant, or who could become pregnant during the study must agree to use condoms with spermicide from the date of the first dose of study drug, throughout the study period, and through 3 months after the last dose of study drug. Total abstinence for the same study period is an acceptable alternative.

The following are considered adequate barrier methods of contraception: diaphragm, condom (by the partner), copper intrauterine device, sponge, or spermicide. Appropriate hormonal contraceptives will include any registered and marketed contraceptive agent that contains an estrogen and/or a progestational agent (including oral, subcutaneous, intrauterine, or intramuscular agents).

Subjects should be informed that taking the study medications may involve unknown risks to the fetus (unborn baby) if pregnancy were to occur during the study. In order to participate in the study, they must adhere to the contraception requirements described above. If there is any question that a subject will not reliably comply with the requirements for contraception, that subject should not be entered into the study.

5.6.3. Use in Pregnancy

If a subject becomes pregnant while on study treatment, the subject will immediately be removed from the study treatment. The site will contact the subject at least monthly and document the subject's status until the pregnancy has been completed or terminated. The outcome of the pregnancy will be reported to HCRN and to Eli Lilly and Company Global Patient Safety and Bristol-Myers Squibb (BMS) Global Pharmacovigilance & Epidemiology immediately and **within 24 hours** if the outcome is a serious adverse experience (e.g., death, abortion, congenital anomaly, or other disabling or life-threatening complication to the mother or newborn). The study investigator will make every effort to obtain permission to follow the outcome of the pregnancy and report the condition of the fetus or newborn to HCRN. If a male subject impregnates his female partner, he must immediately inform the site study personnel and the pregnancy reported to HCRN and to Eli Lilly and Company and BMS Global Pharmacovigilance & Epidemiology, and followed as described above and in Section 11.

5.6.4. Use in Nursing Women

It is unknown whether ramucirumab or nivolumab is excreted in human milk. Since many drugs are excreted in human milk, and because of the potential for serious adverse reactions in the nursing infant, subjects who are breast-feeding are not eligible for enrollment.

6. DOSE DELAYS AND MODIFICATIONS

The NCI Common Terminology Criteria for Adverse Events (CTCAE) Version 4 will be used to grade adverse events. Subjects enrolled in this study will be evaluated clinically and with standard laboratory tests before and at regular intervals during their participation in this study as specified in Section 7. Subjects will be evaluated for adverse events (all grades), serious adverse events, and adverse events requiring protocol therapy interruption or discontinuation at each study visit for the duration of their participation in the study.

Subjects discontinued from the treatment phase of the study for any reason will be evaluated 30 days (\pm 7) after the last dose of protocol therapy.

6.1 Discontinuation Information

If treatment with ramucirumab is unable to restart within 12 weeks of the planned treatment date, the subject will be permanently discontinued from ramucirumab.

NOTE: if either agent is permanently discontinued, treatment with the other agent may continue at the discretion of the investigator.

If treatment with nivolumab is unable to restart within 6 weeks of the planned treatment date, the subject will be permanently discontinued from nivolumab with the following exceptions:

- Dosing delays or interruptions to allow for prolonged steroid tapers to manage drug-related adverse events are allowed. Prior to re-initiating treatment in a subject with a dosing interruption lasting > 6 weeks, the Sponsor Investigator must be consulted.
- Dosing interruptions or delays lasting > 6 weeks that occur for non-drug-related reasons may be allowed if approved by the Sponsor Investigator. Prior to re-initiating treatment in a subject with a dosing interruption lasting > 6 weeks, the Sponsor Investigator must be consulted.

6.2 Management of Infusion-Related Reaction/ Bronchospasm/ Hypersensitivity

NOTE: Since nivolumab contains only human immunoglobulin protein sequences, it is unlikely to be immunogenic and induce infusion or hypersensitivity reactions. However, if such a reaction were to occur, it might manifest with fever, chills, rigors, headache, rash, pruritis, arthralgias, hypo- or hypertension, bronchospasm, or other symptoms of allergic-like reactions.

All Grade 3 or 4 infusion reactions from nivolumab should be reported as an SAE if criteria are met. Infusion reactions should be graded according to NCI CTCAE v4 guidelines.

Table 1A: Management of Infusion Related Reaction (IRR), Allergic Reaction, Hypersensitivity reaction or Bronchospasm from Nivolumab

Description	Action
CTCAE Grade 1 IRR, allergic reaction or bronchospasm¹	Remain at bedside and monitor subject until recovery from symptoms.
CTCAE Grade 2 IRR, allergic reaction or bronchospasm¹	Stop the nivolumab infusion, begin an IV infusion of normal saline, and treat the subject with diphenhydramine 50 mg IV (or equivalent) and/or paracetamol 325 to 1000 mg (acetaminophen); remain at bedside and monitor subject until resolution of symptoms. Corticosteroid or bronchodilator therapy may also be administered as appropriate. If the infusion is interrupted, then restart the infusion at 50% of the original infusion rate when symptoms resolve; if no further complications ensue after 30 minutes, the rate may be increased to 100% of the original infusion rate. Monitor subject closely. If symptoms recur then no further nivolumab will be administered at that visit. Administer diphenhydramine 50 mg IV, and remain at bedside and monitor the subject until resolution of symptoms. The amount of study drug infused must be recorded on the electronic case report form (eCRF).
CTCAE Grade 3 or 4 IRR, allergic reaction, bronchospasm or hypersensitivity reaction²	Immediately discontinue infusion of nivolumab. Begin an IV infusion of normal saline, and treat the subject as follows. Recommend bronchodilators, epinephrine 0.2 to 1 mg of a 1:1,000 solution for subcutaneous administration or 0.1 to 0.25 mg of a 1:10,000 solution injected slowly for IV administration, and/or diphenhydramine 50 mg IV with methylprednisolone 100 mg IV (or equivalent), as needed. Subject should be monitored until the investigator is comfortable that the symptoms will not recur. Nivolumab will be permanently discontinued. Investigators should follow their institutional guidelines

Description	Action
	for the treatment of anaphylaxis. Remain at bedside and monitor subject until recovery from symptoms.

¹For any \leq Grade 2 IRR, allergic reaction or bronchospasm, see Section 5.2 for recommended premedication for subsequent infusions.

²Hypersensitivity reactions included in CTCAEv4 include anaphylaxis, Stevens-Johnson syndrome and toxic epidermal necrolysis; in the case of late-occurring hypersensitivity symptoms (e.g., appearance of a localized or generalized pruritis within 1 week after treatment), symptomatic treatment may be given (e.g., oral antihistamine, or corticosteroids).

Table 1B: Management of Infusion Related Reaction (IRR), Allergic Reaction, Hypersensitivity Reaction or Bronchospasm from Ramucirumab.

Description	Action
CTCAE Grade 1 IRR, allergic reaction or bronchospasm¹	Reduce the infusion rate by 50%.
CTCAE Grade 2 IRR, allergic reaction or bronchospasm¹	Reduce the infusion rate by 50%.
Recurrent CTCAE Grade 2 IRR, allergic reaction or bronchospasm¹	Stop the infusion. Administer additional doses of H1 and H2 blockers intravenously. Administer IV steroids and consider epinephrine and bronchodilators as clinically indicated.
CTCAE Grade 3 or 4 IRR, allergic reaction, bronchospasm or hypersensitivity reaction²	Will be permanently discontinued from ramucirumab.

¹For any \leq Grade 2 IRR, allergic reaction or bronchospasm, see Section 5.2 for recommended premedication for subsequent infusions.

²Hypersensitivity reactions included in CTCAEv4 include anaphylaxis, Stevens-Johnson syndrome and toxic epidermal necrolysis; in the case of late-occurring hypersensitivity symptoms (e.g., appearance of a localized or generalized pruritis within 1 week after treatment), symptomatic treatment may be given (e.g., oral antihistamine, or corticosteroids).

An appropriate resuscitation plan should be in place and a physician readily available during the period of drug administration. If treatment delay necessitates a period longer than 12 weeks for ramucirumab (or 6 weeks for nivolumab [see exceptions in Section 6]), treatment will be stopped and the subject permanently discontinued from the causative agent.

6.3 Dose Modifications

6.3.1 Ramucirumab Dose Modifications

Ramucirumab must be withheld for drug-related toxicities and severe or life-threatening AEs as per Table 2 below. See Section 5.4 for supportive care guidelines. **NOTE:** In addition to the guidelines below, subjects with intolerable or persistent Grade 2 drug-related AE may hold study medication at physician discretion.

Table 2: Ramucirumab dose modification guidelines for drug-related adverse events

Toxicity	Hold Treatment For	Timing for Restarting Treatment	Dose/rate reductions	Discontinue Subject
Proteinuria¹	urine protein levels $\geq 2\text{g}/24\text{hrs}$	once the urine protein level returns to $< 2\text{g}/24\text{hrs}$	Reduce dose to 6 mg/kg per dose for the first occurrence Reduce dose to 5 mg/kg for the second occurrence	For a third occurrence of $>2\text{g}/24\text{hrs}$, or if the protein level does not return to $<2\text{g}/24\text{hrs}$ within 2 weeks
	urine protein level $>3\text{g}/24\text{hrs}$ or in the setting of nephrotic syndrome	Permanently discontinue	Permanently discontinue	Permanently discontinue
Hypertension	Grade 3	Toxicity resolves to Grade 0-2 with medical management	No reduction if toxicity resolves	Permanently discontinue if medically significant hypertension cannot be controlled with antihypertensive therapy.
	Grade 4	Permanently discontinue	Permanently discontinue	Permanently discontinue
Wound healing complications	$\geq\text{Grade 1}$; (NOTE: interrupt drug prior to any scheduled surgery)	Restart when wound is fully healed	No dose reductions warranted	Wound does not heal: permanently discontinue
Reversible posterior leukoencephalopathy syndrome (RPLS)²	Any occurrence	Permanently discontinue	Permanently discontinue	Permanently discontinue
Arterial thrombotic events³	Grade 3 or more severe	Permanently discontinue	Permanently discontinue	Permanently discontinue
Pulmonary embolism (PE) or Venous thromboembolism (VTE)³	Any event that occurs OR worsens despite anticoagulation therapy	Permanently discontinue	Permanently discontinue	Permanently discontinue
Venous thromboembolism (Subjects with unresected primary)	Grade 3-4	When subject has begun anticoagulation	No dose reductions warranted	If in the opinion of the subject's physician, the tumor confers an

Toxicity	Hold Treatment For	Timing for Restarting Treatment	Dose/rate reductions	Discontinue Subject
tumors or local recurrence)³				excessive bleeding risk
Gastrointestinal perforation or fistula formation	Any occurrence	Permanently discontinue	Permanently discontinue	Permanently discontinue
Bleeding	Grade 3-4	Permanently discontinue	Permanently discontinue	Permanently discontinue
Hepatic encephalopathy or other serious signs of liver impairment	Any occurrence	Permanently discontinue	Permanently discontinue	Permanently discontinue
Infusion-related reactions	Grade 3-4	Permanently discontinue	Permanently discontinue	Permanently discontinue
All Other Drug-Related Toxicity	Grade 3 or severe	Toxicity resolves to Grade 0-1	No dose reductions warranted	Toxicity does not resolve within 12 weeks of last dose
	Grade 4 ⁴	Permanently discontinue	No dose reductions warranted	Permanently discontinue

¹ Proteinuria will be monitored by urine dipstick and/or urinary protein creatinine ratio for the development of worsening of proteinuria during ramucirumab therapy.

² All cases of RPLS must be reported via the SAE mechanism.

³ Any venous or arterial event leading to discontinuation of ramucirumab therapy will be considered serious and should be reported via the serious adverse event (SAE) mechanism.

⁴ The following events do not require discontinuation: lab alterations or Grade 4 fever.

NOTE: Permanently discontinue for any severe or Grade 3 drug-related AE that recurs or any life-threatening event.

6.3.2 Nivolumab Dose Delay Criteria

Adverse events (both non-serious and serious) associated with nivolumab exposure may represent an immunologic etiology. These adverse events may occur shortly after the first dose or several months after the last dose of treatment. Nivolumab must be withheld for drug-related toxicities and severe or life-threatening AEs as per Table 3 below. See Section 5.4 for supportive care guidelines, including use of corticosteroids. **NOTE:** In addition to information in the table, permanently discontinue for any severe or Grade 3 drug-related AE that recurs or any life-threatening event. Subjects with intolerable or persistent Grade 2 drug-related AE may have study medication held at physician discretion. Permanently discontinue study drug for persistent Grade 2 adverse reactions for which treatment with study drug has been held, that do not recover to Grade 0-1 within 6 weeks of the last dose unless delay beyond 6 weeks allows for prolonged steroid taper to manage toxicity. In such cases, the Sponsor Investigator must be consulted prior to re-initiating treatment.

Table 3: Nivolumab dose modification guidelines for drug-related adverse events

Toxicity	Hold Treatment For	Timing for Restarting Treatment	Discontinue Subject
Diarrhea/Colitis	Grade 2-3	Toxicity resolves to Grade 0-1	Toxicity does not resolve within 6 weeks of last dose unless delay beyond 6 weeks allows for prolonged steroid taper to manage toxicity. In such cases, the Sponsor Investigator must be consulted prior to re-initiating treatment.
	Grade 4	Permanently discontinue	Permanently discontinue
Pneumonitis	Grade 2	Toxicity resolves to Grade 0-1	Toxicity does not resolve within 6 weeks of last dose unless delay beyond 6 weeks allows for prolonged steroid taper to manage toxicity. In such cases, the Sponsor Investigator must be consulted prior to re-initiating treatment.
	Grade 3-4	Permanently discontinue	Permanently discontinue
Hepatitis	≥ Grade 2 if subject has baseline AST, ALT or total bilirubin that is within normal limits; ≥ Grade 3 if subject has baseline AST, ALT or total bilirubin within the Grade 1 toxicity range	Toxicity resolves to Grade 0-1	Toxicity does not resolve within 6 weeks of last dose unless delay beyond 6 weeks allows for prolonged steroid taper to manage toxicity. In such cases, the Sponsor Investigator must be consulted prior to re-initiating treatment.
	AST or ALT > 8 x ULN OR total bilirubin >5 x ULN OR concurrent AST or ALT > 3 x ULN and total bilirubin > 2 x ULN	Permanently discontinue	Permanently discontinue
Type I diabetes mellitus [T1DM] (if new onset) or Hyperglycemia	New onset T1DM or Grade 3 hyperglycemia	Toxicity resolves to Grade 0-1 even if requires physiologic hormone replacement	Resume nivolumab when subjects are clinically and metabolically stable.
	Grade 4	May need to permanently discontinue; see footnote #4	May need to permanently discontinue; see footnote #4
Hypophysitis	Grade 2-3	Toxicity resolves to Grade 0-1	Toxicity does not resolve within 6 weeks of last dose unless delay beyond 6 weeks allows for prolonged steroid taper to manage toxicity. In such cases, the Sponsor Investigator must be consulted prior to re-initiating treatment.

Toxicity	Hold Treatment For	Timing for Restarting Treatment	Discontinue Subject
	Grade 4	Permanently discontinue	Permanently discontinue
Nephritis and Renal Dysfunction	Serum creatinine more than 1.5 and up to 6 times the upper limit of normal	Toxicity resolves to Grade 0-1	Toxicity does not resolve within 6 weeks of last dose unless delay beyond 6 weeks allows for prolonged steroid taper to manage toxicity. In such cases, the Sponsor Investigator must be consulted prior to re-initiating treatment.
	Serum creatinine more than 6 times the upper limit of normal	Permanently discontinue	Permanently discontinue
Skin	Grade 3 rash or suspected Stevens-Johnson syndrome (SJS) or toxic epidermal necrolysis (TEN)	Toxicity resolves to Grade 0-1	Toxicity does not resolve within 6 weeks of last dose unless delay beyond 6 weeks allows for prolonged steroid taper to manage toxicity. In such cases, the Sponsor Investigator must be consulted prior to re-initiating treatment.
	Grade 4 or confirmed SJS or TEN	Permanently discontinue	Permanently discontinue
Encephalitis	New-onset moderate or severe neurologic signs or symptoms	Toxicity resolves to Grade 0-1	Toxicity does not resolve within 6 weeks of last dose unless delay beyond 6 weeks allows for prolonged steroid taper to manage toxicity. In such cases, the Sponsor Investigator must be consulted prior to re-initiating treatment.
	Immune-mediated encephalitis	Permanently discontinue	Permanently discontinue
Adrenal Insufficiency	Grade 2	Toxicity resolves to Grade 0-1 even if requires physiologic hormone replacement	Toxicity does not resolve within 12 weeks of last dose.
	Grade 3-4	May need to permanently discontinue; see footnote #4	May need to permanently discontinue; see footnote #4
Uveitis ¹	≥Grade 2	Permanently discontinue	Permanently discontinue
Thrombocytopenia	Grade 3 >7 days or associated with bleeding or Grade 4	Permanently discontinue	Permanently discontinue
All Other Drug-Related Toxicity	Grade 2 ²	Toxicity resolves to Grade 0-1 even if requires physiologic hormone replacement for drug related endocrinopathy	Toxicity does not resolve within 6 weeks of last dose unless delay beyond 6 weeks allows for prolonged steroid taper to manage toxicity. In such cases, the Sponsor Investigator must be consulted

Toxicity	Hold Treatment For	Timing for Restarting Treatment	Discontinue Subject
			prior to re-initiating treatment.
	Grade 3 or severe	Toxicity resolves to Grade 0-1 even if requires physiologic hormone replacement for drug related endocrinopathy	Toxicity does not resolve within 6 weeks of last dose unless delay beyond 6 weeks allows for prolonged steroid taper to manage toxicity. In such cases, the Sponsor Investigator must be consulted prior to re-initiating treatment.
	Grade 4 ⁴	Permanently discontinue	Permanently discontinue

¹ Uveitis or blurred vision that does not respond to topical therapy and does not improve to Grade 1 severity within the re-treatment period OR requires systemic treatment

² Exceptions include grade 2 drug-related fatigue or laboratory abnormalities; do not delay for these events.

³ Exceptions include grade 3 lymphopenia or leukopenia; do not delay for these events. In addition, any Grade ≥ 3 drug-related amylase or lipase abnormality that is not associated with symptoms or clinical manifestations of pancreatitis does not require dose delay. The Investigator should be consulted for such Grade ≥ 3 amylase or lipase abnormalities.

⁴ The following events do not require discontinuation:

- Isolated Grade 4 amylase or lipase abnormalities that are not associated with symptoms or clinical manifestations of pancreatitis and decrease to < Grade 4 within 1 week of onset.
- Isolated Grade 4 electrolyte imbalances/abnormalities that are not associated with clinical sequelae and are corrected with supplementation/appropriate management within 72 hours of their onset
- Grade 4 lymphopenia or leucopenia
- Grade 4 drug-related endocrinopathy adverse events, such as adrenal insufficiency, ACTH deficiency, hyper- or hypothyroidism, or glucose intolerance, which resolve or are adequately controlled with physiologic hormone replacement (corticosteroids, thyroid hormones) or glucose-controlling agents, respectively, may not require discontinuation after discussion with and approval from the Investigator.

NOTE: Permanently discontinue for any severe or Grade 3 drug-related AE that recurs or any life-threatening event.

Subjects with intolerable or persistent Grade 2 drug-related AE may hold study medication at physician discretion. Permanently discontinue study drug for persistent Grade 2 adverse reactions for which treatment with study drug has been held, that do not recover to Grade 0-1 within 12 weeks of the last dose.

Dosing interruptions are permitted in the case of medical / surgical events or logistical reasons not related to study therapy (e.g., elective surgery, unrelated medical events, subject vacation, and/or holidays). Subjects should be placed back on study therapy within 12 weeks of the scheduled interruption, unless otherwise discussed with the HCRN Project Manager. The reason for interruption should be documented in the subject's study record.

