Neurologic AEs have been uncommonly observed following treatment with nivolumab. The frequency of neurologic AEs may be greater with nivolumab + ipilimumab combination therapies than with nivolumab monotherapy or other nivolumab combinations. Neurologic AEs can manifest as central abnormalities (e.g., aseptic meningitis, encephalopathy, or encephalitis) or peripheral sensory/motor neuropathies (e.g., Guillain-Barre Syndrome, myasthenia gravis complicated with sepsis and fatality). The onset has been observed as early as after a single treatment with the nivolumab + ipilimumab combination.

Infusion Reactions

Infusion reactions, including high-grade hypersensitivity reactions, following administration of nivolumab are uncommon. Investigators are advised to monitor for fever, chills, shakes, itching, rash, hypertension or hypotension, or difficulty in breathing during and immediately after administration of nivolumab.

Lipase/Amylase Elevations

Asymptomatic elevations in lipase and amylase have been reported. In monotherapy studies, lipase and amylase levels were not systematically monitored, so an estimate of the frequency of asymptomatic lipase/amylase elevations is unknown. In studies evaluating the safety of the nivolumab + ipilimumab combination in multiple tumor types, lipase and amylase levels were systematically monitored, and elevations in any grade of lipase/amylase were consistently noted in approximately 10% to 30% of subjects. Very few subjects reported associated symptoms (e.g., abdominal pain) or radiographic findings (e.g., stranding) consistent with pancreatitis. Thus, there does not seem to be clinical significance to the elevated laboratory values.

Uveitis and Visual Complaints

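### The rule that stops nivolumab for good when a Grade 3 drug-related event recurs makes no exception for the laboratory events that Table 3, footnote 3 says need no dose delay

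*Combined protocol and SAP*

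**What the plan says.** All the governing text is in section 6.3.2 of the protocol.

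- The paragraph before Table 3 sets a recurrence rule on top of the table: "In addition to information in the table, permanently discontinue for any severe or Grade 3 drug-related AE that recurs or any life-threatening event".
- The text after the footnotes repeats it: "NOTE: Permanently discontinue for any severe or Grade 3 drug-related AE that recurs or any life-threatening event". Neither statement mentions a footnote or names an exception.
- Footnote 3 covers Grade 3 blood counts: "Exceptions include grade 3 lymphopenia or leukopenia; do not delay for these events". It then says that a drug-related amylase or lipase abnormality of Grade 3 or higher, without symptoms or signs of pancreatitis, needs no dose delay, and that the Investigator should be consulted about it.
- Footnote 4 lists events that need not lead to discontinuation. One entry is "Grade 4 lymphopenia or leucopenia", with no condition attached. Another is an isolated Grade 4 amylase or lipase abnormality without pancreatitis that falls below Grade 4 within 1 week.

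Section 10.2.9 bears on intent in two places. On amylase and lipase it concludes: "Thus, there does not seem to be clinical significance to the elevated laboratory values". In its paragraph on other immune-mediated events, it limits the recurrence stop to severe immune-related reactions and describes it after a cycle of withholding and resuming.

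**The concern.** An event judged too unimportant to delay a dose should not, merely by happening twice, end the drug. The recurrence rule does that for the two footnote 3 groups. The stop is permanent and removes one of the two agents under test; under section 6.1 the other may continue only at the investigator's discretion. For the subject concerned, nivolumab would be lost over a laboratory finding that the protocol itself treats as unimportant, at least for amylase and lipase.

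**Working it through.** No figure in the plan depends on this point and no arithmetic applies. The check is to follow each footnote 3 event through the rules as written, assuming it has been recorded as a drug-related adverse event.

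| Event | Rule that applies | Result for nivolumab |
|---|---|---|
| Grade 3 lymphopenia/leukopenia, first episode | Footnote 3 | No delay |
| Grade 3 lymphopenia/leukopenia, recurring | Recurrence note | Permanent stop |
| Grade 4 lymphopenia/leukopenia | Footnote 4 | Stop not required |
| Grade 3 amylase/lipase without pancreatitis, first episode | Footnote 3 | No delay; Investigator consulted |
| Grade 3 amylase/lipase without pancreatitis, recurring | Recurrence note | Permanent stop |
| Grade 4 amylase/lipase, isolated, without pancreatitis, below Grade 4 within 1 week | Footnote 4 | Stop not required |
| Recurring Grade 4 form of either | Footnote 4, or the note if the event counts as *severe* | Unclear |

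**Does a footnote already override the note?** Footnote 3 deals with delay and says nothing about discontinuation. Footnote 4 deals with discontinuation, but for these two groups only at Grade 4. Neither mentions recurrence. The first statement of the note is expressly additional to the table. No other section exempts the footnote 3 events.

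**Can the events reach the rule?** The laboratory lines of the section 7 calendar cover platelets, neutrophils and hemoglobin, and a chemistry panel listed in calendar footnote 3. Lymphocytes, total white count, amylase and lipase appear in neither. Section 11.1.2 asks for documentation of laboratory results that are clinically significant, that meet the definition of a serious event or drug-induced liver injury, that lead to interruption or discontinuation, or that need corrective therapy. An untreated, asymptomatic value may therefore go unrecorded. The rule applies only when the abnormality is found outside the scheduled tests, is recorded as an adverse event and is attributed to the drug, and this happens twice.

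**The case against.** The strongest reply is that the parts can be read in harmony. Footnote 4 does not confine itself to first episodes, so its exceptions could be taken to qualify the general note and, by implication, to cover the milder grade. An investigator might also say that an event for which dosing was never withheld cannot recur in the sense of section 10.2.9, since the protocol does not define the word. Both readings are sensible, but the text states neither, and a site following the words would stop the drug.

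Other parts of the reply stand, and they limit the point.

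- **Grade 3 against Grade 4.** A reader might infer that the plan is always harsher on Grade 3 than on Grade 4. That compares a recurring Grade 3 event with a Grade 4 event whose recurrence is not addressed. The note also covers *severe* events, so a recurring Grade 4 event may be caught as well.
- **Electrolytes, glucose and adrenal events.** A reader might extend the point to these. For Grade 3 hyperglycemia the table says "Resume nivolumab when subjects are clinically and metabolically stable", and Grade 3 electrolyte events are held until they resolve. Holding, resuming, and stopping on recurrence is a coherent escalation and a clinical choice. The adrenal row for Grades 3 and 4 says "May need to permanently discontinue; see footnote #4" while that footnote names only Grade 4 endocrine events. This is loose cross-referencing and does not show the same no-delay-then-stop pattern.
- **Ramucirumab.** Table 2, footnote 4 exempts laboratory alterations without giving a grade, above a similar recurrence note. The most that can be said is that its reach is unclear.
- **Frequency.** Section 10.2.9 reports that "elevations in any grade of lipase/amylase were consistently noted in approximately 10% to 30% of subjects". That figure is for nivolumab with ipilimumab, at any grade and under systematic testing, and the same paragraph calls the monotherapy frequency unknown. It does not estimate recurring Grade 3 events here.

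**Conclusion.** Wrong as written, minor. The recurrence note, in both places, ends nivolumab permanently for a recurring Grade 3 lymphopenia, leukopenia, or amylase or lipase abnormality without pancreatitis, although footnote 3 says such an event does not warrant a delayed dose. The point holds for those two groups only.

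The conclusion rests on reading the note literally and on the event being recorded as a drug-related adverse event. The documents give no rate for such recurrences. The frequency is probably low, because the relevant tests are not scheduled.

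A reader might infer a loss of power or a bias in the response rate, or count all the remaining cycles of the 52 as lost. The documents support neither. There is no rate from which to derive an effect on response, and a count of remaining cycles would assume that treatment otherwise ran the full 24 months, whereas progression or toxicity can end it sooner.

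**What to change.** In both nivolumab notes in section 6.3.2 (before Table 3 and after its footnotes), insert directly after the words on recurrence: *(except the events listed in footnote 3, which are managed at each recurrence as at first occurrence, and Grade 4 events that meet the conditions of footnote 4)*. Leave the clause on life-threatening events and every table row unchanged. A Grade 4 amylase or lipase value that does not fall below Grade 4 within 1 week would then still stop nivolumab under the Grade 4 row.

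If the sponsor does intend to stop these events on recurrence, one sentence saying so would settle the matter instead.

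The cost is a wording amendment to two notes, with no added patients, visits or procedures. The small downside is that a few subjects would continue nivolumab after a recurring asymptomatic laboratory event; the life-threatening clause and the Grade 4 rows remain as protection.
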